4.3.2.2 Microarray Analysis

For microarray-based assays, we will follow an approach that we have successfully used in our past work¹⁰ with modifications to incorporate updates to the Affymetrix GeneChip technology. Total RNA (50-100 ng) will be amplified using the SensationPlus FFPE Amplification kit (Affymetrix, Inc.) with QC to assess the quantity and quality of the final

amplified product. We will use the Affymetrix GeneChip Human Transcriptome Array 2.0 for performing gene expression profiling of the PEL RNA. Following amplification of the RNA specimen, the sample will be hybridized, labeled with the WT Labeling Kit (Affymetrix, Inc.), washed, and scanned as per the Affymetrix protocol. Spike-in hybridization controls will facilitate data normalization between specimens. Normalization of array CEL files will be carried out using the gcrma software from the Bioconductor suite (http://www.bioconductor.org). The percent present calls and 3'/5' ratio of GAPDH will be determined for each sample. Samples with less than 25% presents calls will be considered technical failures. This methodology is specifically meant for GeneChip assay of small amounts of partially degraded RNA from clinical samples.

4.3.2.3 Analytic Strategy

RNA-Seq assay of PEL is the preferred approach because it has a better linear dynamic range than does a GeneChip assay and may provide insights about PEL genomics that are not possible to be discerned by GeneChipbased expression profiling (i.e., novel splice junctions and transcripts, viral RNAs, etc.). However, because of the high likelihood of very substantial RNA degradation in these FFPE samples, we are concerned about the potential for poor quality RNA-Seq data. RNA-Seq will be the primary method for genomic analysis of the PEL specimens, if it satisfies QC metrics for read number and data quality (i.e., 30 million pair-end reads of length > 30 nucleotides, of which 20-25 million may be mapped to the genome or known transcriptome; R^2 (Pearson) correlation between technical replicates of the same sample of > 0.9). If the QC metrics are not met, GeneChip assay will be performed instead, as these should yield higher quality data. In summary, GeneChip assay is planned as a backup in the event that RNA-Seq QC is inadequate.

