4.3.2 RNA-Seq and Microarray Analysis of RNA

4.3.2.1 RNA-Seq Analysis

For RNA-Seq assays we will use Illumina's TruSeq RNA Access Library Prep Kit to generate RNA libraries. This reagent kit, which focuses on transcriptome coding regions, can be performed with as little as 20ng of degraded total RNA isolated from FFPE specimens. RNA libraries will be multiplexed and, following cluster generation, sequenced with 100 basepair (bp) single end (SE) reads to a depth of approximately 45 million reads per sample on an Illumina HiSeq2000 instrument. To mitigate assay noise we will perform RNA-Seq on each PEL RNA sample in triplicate, using an independently generated library for each RNA-Seq assay. Each sample will be barcoded and sequenced as part of a single pool with up to 30 samples loaded onto an 8-lane flow cell.

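### The quality gate that selects the genomic platform counts paired-end reads, but the specified assay is single-end, and the counting unit is not stated

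*Combined protocol and SAP*

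**What the plan says.** Section 4.3.2.1 of the protocol describes the assay. Libraries are "sequenced with 100 basepair (bp) single end (SE) reads to a depth of approximately 45 million reads per sample", and each RNA sample is assayed in triplicate with an independently prepared library each time. Trimmed reads shorter than 20 base pairs are discarded. RNA-Seq is run on 20 specimens, 10 from long-term survivors and 10 from others, and the data are then assessed for quality and adequacy.

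Section 4.3.2.3 sets the gate: "RNA-Seq will be the primary method for genomic analysis of the PEL specimens, if it satisfies QC metrics for read number and data quality". The metrics given are:

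- "30 million pair-end reads of length > 30 nucleotides";
- "of which 20-25 million may be mapped to the genome or known transcriptome";
- an R^2 (Pearson) "correlation between technical replicates of the same sample of > 0.9".

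The consequence of failure is explicit: "If the QC metrics are not met, GeneChip assay will be performed instead". The section describes GeneChip as a backup and prefers RNA-Seq for its linear dynamic range and for what it can show about splice junctions, novel transcripts and viral RNA.

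Section 5.1.1 says that one assay or the other will be performed, on up to 80 specimens. No section describes a paired-end run, a second read, or a conversion between single-end and paired-end counts.

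**The concern.** The gate is written for a type of read that the assay does not produce, and it decides which platform answers the primary genomic objective in Section 1.2. Applied to the letter, it sends the study to the less preferred platform whatever the data quality. Applied with an unwritten correction, its result depends on which correction is chosen, because neither the 45 million nor the 30 million is tied clearly to a library or to a specimen.

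Borderline results are foreseeable. Section 4.3.2.3 itself expects heavy RNA degradation in the fixed specimens. The 20 specimens assessed first also equal the minimum genomics enrolment in Section 3.3.1, so they could turn out to be the whole analysis set. An unclear gate would then be interpreted with those data already in hand.

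**Working it through.** The plan gives no derived figure to reproduce, so the check compares the assay's planned output with the gate.

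**Inputs**

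- Read type: single-end, 100 bp (Section 4.3.2.1).
- Depth: about 45 million reads per sample (Section 4.3.2.1).
- Libraries: 3 per RNA sample (Section 4.3.2.1).
- Gate: 30 million paired-end reads, 20 to 25 million mapped, R^2 above 0.9 (Section 4.3.2.3).

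**Step 1: literal reading.** A single-end run gives 0 paired-end reads. 0 < 30 million, so the gate fails whatever the depth.

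**Step 2: non-literal readings.** Three things are open:

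- the gate is 30 million individual reads, or 30 million pairs (2 × 30 = 60 million reads);
- the gate applies per library or per specimen;
- the 45 million applies per library (3 × 45 = 135 million per specimen) or per specimen (45 / 3 = 15 million per library, assuming equal shares).

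Ratio = planned reads / required reads, both in the unit of the gate:

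| Gate | 45 million per library | 45 million per specimen |
|---|---|---|
| 30 million reads per library | 45/30 = 1.5, pass | 15/30 = 0.5, fail |
| 30 million reads per specimen | 135/30 = 4.5, pass | 45/30 = 1.5, pass |
| 60 million reads per library | 45/60 = 0.75, fail | 15/60 = 0.25, fail |
| 60 million reads per specimen | 135/60 = 2.25, pass | 45/60 = 0.75, fail |

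Four of the eight combinations pass on planned count and four fail.

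**Step 3: margin under the plainest reading.** With 30 million single reads required and 45 million planned in the same unit, the tolerable loss is 1 − 30/45 = 33%. The gate counts reads longer than 30 nucleotides while the pipeline keeps reads of 20 base pairs or more. The two are compatible, but the gate count is taken on a smaller subset than the retained reads.

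**Step 4: the other metrics.** The mapped figure is 20/30 = 67% to 25/30 = 83% of the 30 million, given as a range with a permissive verb. If R^2 > 0.9 is meant, Pearson r must exceed √0.9 = 0.949. If the 0.9 is r itself, R^2 need only exceed 0.9² = 0.81.

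**The case against.** The strongest reply is that the paired-end wording is an evident slip, or a threshold carried over from a paired-end design. Sequencing at 45 million single-end reads clears a plain 30-million threshold with room to spare, and the most natural match to the per-sample depth (both figures per specimen) passes at 1.5. A sensible team would not abandon RNA-Seq over one word. This is plausible, and it limits the harm. It does not remove the need for correction: the repair is not unique, and half of the readings in the table fail.

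A reader might infer that platforms will be mixed specimen by specimen, confounding platform with RNA quality. The documents lean the other way. Section 5.1.1 presents the two assays as alternatives, Section 4.3.2.3 speaks of a primary method and a backup, and Section 4.3.2.1 has a 20-specimen stage followed by a quality assessment. Together these point to one switch for the study. What stands is that no sentence says so.

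A reader might also infer that the platform could be chosen to suit the survival result. The listed metrics are read count, mapping and replicate correlation; none is the survival contrast, and any sequencing quality gate is judged after the data exist. The documents show no mechanism by which the read-type wording biases that comparison.

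The mapped-read range has an obvious lower bound of 20 million, and R^2 above 0.9 has an ordinary meaning. These two points are clarifications, not separate faults.

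**Conclusion.** The contradiction between Sections 4.3.2.1 and 4.3.2.3 is real, stands in the current text and is not resolved elsewhere. As written, the gate cannot be met. Once the literal reading is set aside, the planned depth is between 0.25 and 4.5 times the requirement. With both figures in the same unit, it is 1.5 times (pass) if single reads are counted and 0.75 times (fail) if pairs are counted. These ratios use planned depth with no read loss and, where depth is shared, an equal split across three libraries.

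Two stronger conclusions might be drawn, and neither is supported. The mismatch does not show that RNA-Seq is infeasible, since the planned depth passes under several reasonable readings. Nor is there just one reading that passes.

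The point should be fixed because the rule governs a primary objective. It is not a fatal flaw: this is a retrospective case series, a backup platform is specified, and no error rate, sample size or clinical objective depends on the wording.

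**What to change.** Reconcile Sections 4.3.2.1 and 4.3.2.3 in one edit:

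1. State one read type in both sections.
2. State one counting unit, library or specimen, for both the 45 million depth and the 30 million gate. For example: at least 30 million single-end reads of more than 30 nucleotides, in the same unit as the 45 million. The documents do not settle which unit was meant, so the sponsor must choose.
3. Give 20 million as the mapped-read minimum, and define the replicate criterion as R^2 > 0.9, that is, Pearson r > 0.949.
4. Confirm that the switch to GeneChip is a single study-level decision, taken on the 20-specimen stage from quality metrics only, in line with the either-or wording of Section 5.1.1.

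The four items cost protocol wording only and keep the plan's own thresholds. One matter needs separate alignment: Section 3.3.3 allows replacement for insufficient specimens or insufficient genetic material, but does not cover a specimen that fails sequencing quality control. Dropping or replacing such specimens would need that rule extended, or would lose cases in a rare disease with a genomics minimum of 20.

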5.0 STATISTICAL CONSIDERATIONS

5.1 Study Design/Endpoints

5.1.1 Analysis/Statistics

Survival will be estimated using the Kaplan Meier method and Cox proportional hazards model will be used to assess differences between treatment groups and categorical baseline variables. Response rates will be reported with 95% confidence intervals (binomial distribution). Descriptive statistics will be used to summarize baseline clinical, histological, and viral characteristics.

We will perform either RNA-Seq or GeneChip assays, as described in Section 4.3, expression profiling on a total of up to 80 AIDS-PEL specimens. We are already aware of at least 10 long -term AIDS-PEL survivors within the AMC. Resultant data will be assessed for quality, normalized, and then analyzed for differential gene expression. We will use standard algorithms in both GeneSpring and Bioconductor for this purpose, with which we have considerable experience (see Preliminary Studies above). In particular, the RNA-Seq data will be analyzed by the DESeq algorithm in Bioconductor¹. Lastly, we will take advantage of bioinformatic analysis approaches to help make sense of possible biological links between the genes found to be differentially expressed between the sample groups that may be of prognostic significance. These bioinformatic approaches, such as Ingenuity Pathways (http://www.ingenuity.com), focus on the analysis of genetic networks and pathways and help place genes identified as differentially expressed into biologic context.

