2.0 BACKGROUND

2.1 Study Disease

Primary effusion lymphoma (PEL) is a rare type of non-Hodgkin lymphoma (NHL) that presents with predominately body cavity involvement and is nearly universally associated with Kaposi's sarcoma herpesvirus (KSHV), with Epstein Barr virus (EBV) also present in a fraction of cases¹. PEL is typically associated with a poor prognosis with a median survival of 6 months². A solid variant has also been described and carries a similarly poor prognosis³. PEL typically arises in the context of HIV infection, where it accounts for approximately 2-3% of AIDS-NHL².

Data supporting optimal treatment strategies of PEL are limited given the rarity of the disease. There are rare reports of remissions in PEL occurring with the introduction of HAART therapy in HIV patients, who are not on highly active antiretroviral therapy (HAART) at the time of diagnosis. However, HAART is not sufficient for adequate treatment in the vast majority of AIDS-PEL cases. Therefore, combined chemotherapy regimens and other anti-viral treatments are now routinely used for AIDS-PEL treatment. In addition to classic CHOP-based chemotherapy, clinicians and investigators have employed one or more of the following: (a) infusional chemotherapy regimens (EPOCH); (b) methotrexate (after chemotherapeutic debulking or drainage of effusions); (c) VEGF inhibition, aggressive effusion drainage; (d) taken advantage of latent gamma herpes virus tumor infection using bortezomib as an inducer of lytic viral replication and an inhibitor of $NF-kB^4$; and (e) cidofovir or valganciclovir as inhibitors of KSHV replication, with or without interferon⁵. Auto- and allo-geneic hematopoietic stem cell transplant is also reported in the salvage setting with variable success. Long-term AIDS-PEL survivors have been reported², some of whom are being followed at UCSD as well as by collaborators at other institutions within the AMC.

Most of the literature on AIDS-PEL is in the form of single or small case reports, with the largest series including 28 participants reported from a French cohort in 2005^2 . This series explored baseline clinical factors associated with poor survival and identified ECOG performance status > 2 and lack of HAART use at time of diagnosis as independent predictors of shorter survival. A recent review of case in the literature identified the number of body cavity sites as predictive of survival⁶.

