3.1 Eligibility Criteria

Patients diagnosed with primary effusion lymphoma (HIV seropositive or negative) on or after January 1, 1998 on whom survival status at 2 years post PEL diagnosis is available.

Participants may be enrolled to *either or both* the clinical or genomic portions of the study.

The minimum data required to be able to include a participant for analysis of **clinical prognostic factors** are:

- a. HIV status, and for HIV-positive participants, include CD4 count, HIV viral load within one year prior PEL diagnosis (or within 3 months after PEL diagnosis)
- b. Age at PEL diagnosis
- c. Gender
- d. Stage at PEL diagnosis
- e. Treatment of PEL
- f. Response to PEL treatment
- g. Survival status at 2 years post diagnosis
- h. Pathology slides (or paraffin block) for central review
- i. Year of PEL diagnosis

The minimum data required to be able to include a participant for analysis of **genomic prognostic factors** are:

- a. Availability of a pathologic specimen of PEL that will be submitted for genomic analysis
- b. Survival status at 2 years post diagnosis

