3.3 Number of Participants to be Enrolled

A survey of investigators participating in the AMC consortium regarding the number of PEL patients seen at their site in the last 5 years reported 23 participants from 11 responding sites. By including the last 13 years (HAART era), it is reasonable to expect approximately 80 participants especially considering new sites added to the AMC.

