4.2 Study Plan

- 4.2.1 Data, Documents, Records, or Specimen Identification:
 - 4.2.1.1 The following data will be collected for participants enrolled into the clinical portion of the study:
 - HIV status, and for HIV-positive participants, include CD4 count, HIV viral load within one year prior PEL diagnosis (or within 3 months after PEL diagnosis)
 - Age at PEL diagnosis
 - Gender
 - Stage at PEL diagnosis
 - Treatment of PEL
 - Best response to PEL treatment
 - Survival status at 2 years post diagnosis
 - Pathology slides for central review (See Appendix II for specimen preparation and shipping)
 - Year of PEL diagnosis
 - 4.2.1.2 The following will be collected for participants enrolled into the genomics portion of the study:
 - Pathology slides for central review (if unavailable, paraffin block may be submitted)
 - Pathologic specimen that will be submitted for genomic analysis:
 - Frozen specimens, formalin-fixed and paraffin-embedded (FFPE) demonstrating PEL including cytospins as well as any mass/nodal biopsies are acceptable (See Appendix II for specimen preparation and shipping)
 - Survival status at 2 years post diagnosis
 - 4.2.1.3 The following is a list of additional data that is highly desirable for inclusion whenever available for participants enrolled in either the clinical and/or genomics portion of the study:
 - Race and ethnicity
 - For participants with HIV: HIV treatment history (which HAART drugs has participant received prior to PEL diagnosis, after PEL diagnosis), baseline HIV characteristics (i.e., CD4 count and HIV viral load closest

to time of PEL diagnosis, history of opportunistic infections)

- Presence or history of other human herpesvirus-8 (HHV-8)-related diseases (i.e., Kaposi's sarcoma, Multicentric Castleman's Disease), and other malignancies)
- Lymphoma baseline disease characteristics (immunophenotype, Epstein-Barr virus (EBV) and Kaposi sarcoma herpes virus (KSHV) status, sites of extranodal involvement), and either IPI or data required for calculation of International Prognostic Index (IPI)
- Lymphoma treatment: type, number of treatment regimens, use of therapeutic effusion drainage
- Best response to PEL treatment, best response duration
- Survival status at time of enrollment and duration of survival in months from PEL diagnosis

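### Survival is counted from PEL diagnosis with ordinary Kaplan-Meier and Cox, but the plan neither records nor allows for cases that first reached the AMC site after diagnosis

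*Combined protocol and SAP*

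**What the plan says.** The survival analysis is one sentence in 5.1.1: "Survival will be estimated using the Kaplan Meier method and Cox proportional hazards model will be used to assess differences between treatment groups", extended there to categorical baseline variables. The section names no time origin and does not mention delayed entry, landmark analysis or time-dependent treatment.

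The origin has to be taken from the data list in 4.2.1.3, which asks for "Survival status at time of enrollment and duration of survival in months from PEL diagnosis". That item is listed as highly desirable, not required.

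Eligibility in 3.1 covers patients diagnosed "on or after January 1, 1998 on whom survival status at 2 years post PEL diagnosis is available". It does not say where the diagnosis was made or how soon the patient came to the enrolling site. The feasibility survey in 3.3 counted the "number of PEL patients seen at their site in the last 5 years reported 23 participants from 11 responding sites", so it counted patients seen at a site, not patients diagnosed there.

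Neither the minimum data in 3.1 nor the lists in 4.2.1.1 to 4.2.1.3 include the date first seen at the enrolling site or the date each treatment began. Treatment strategy is part of the primary clinical objective (1.2).

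**The concern.** A patient diagnosed elsewhere and referred some months later enters the AMC site's charts only if still alive at referral. A comparable patient who died before referral leaves no AMC record. Ordinary Kaplan-Meier and Cox place the referred patient at risk from month 0, so the months before the first visit count as follow-up in which that record could not have ended in death. This is left truncation.

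Two things are at stake. Median and 2-year survival would be too high. A treatment given more often to late-entering cases would also gain an advantage that it did not earn. The second matters more, because comparing treatments is part of the primary clinical objective. In a disease with a stated median survival of 6 months (2.1), a delay of a few months is not small.

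The problem would arise even with a full consent waiver and complete chart review at every site. It is therefore separate from the selection of known survivors.

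**Working it through.** **Inputs from the documents.** Median survival 6 months (2.1); 80 participants (3.3.1); survival counted from diagnosis (4.2.1.3).

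**Assumptions, not in the documents.** Exponential survival, the share of cases referred late, the delay, and how closely treatment follows referral. The plan states no alpha, power or hazard ratio for the survival analysis, so there is no design figure to reproduce. The only related figures are expected long-term survivors: 25-40% of 80 = 20-32 (4.3.1, which reproduces) and 15-25% of 80 = 12-20 (5.2). That disagreement is a separate matter.

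**Step 1: true survival.** S(t) = 2^(-t/6), so S(24) = 2^(-4) = 6.25%, or 5 of 80.

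**Step 2: every case enters at delay d.** Naive S(24) = 2^(-(24-d)/6) and naive median = 6 + d.

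| d (months) | Naive 2-year survival | Naive median (months) |
|---|---|---|
| 1 | 7.0% | 7 |
| 2 | 7.9% | 8 |
| 3 | 8.8% | 9 |
| 6 | 12.5% | 12 |

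**Step 3: only a share enters late.**
- 30% enter at 6 months. Naive S(24) = 0.70 × 6.25% + 0.30 × 12.5% = 8.1%. Beyond month 6 the naive curve is (0.70 + 0.30 × 2) × 2^(-t/6) = 1.3 × 2^(-t/6), which reaches 0.5 at t = 6 × log2(2.6) = 8.3 months.
- 20% enter at 3 months. Naive S(24) = 0.80 × 6.25% + 0.20 × 8.8% = 6.8%, with a median of 6.7 months.
- With 25-50% referred and exponential delays of mean 1 to 6 months, simulation moves 2-year survival by at most about 2 percentage points and the median by 0.3-1.9 months. Delayed-entry risk sets bring the median back to 6.0-6.1 months.

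**Step 4: a treatment with no effect (true HR 1).** 80 cases, 24 referred, two-sided 5% test, simulated.

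| Who is treated | Delay | Naive HR | Naive false-positive rate |
|---|---|---|---|
| 60% of referred, 20% of others | fixed 3 months | about 0.90 | about 5-8% |
| 60% of referred, 20% of others | fixed 6 months | about 0.82 | about 14% |
| All referred, no others | exponential, mean 3 to 6 months | about 0.77 to 0.66 (large sample, 25% referred) | about 14-32% |
| All referred, no others | fixed 3 months | about 0.70-0.73 | about 22-24% |
| All referred, no others | fixed 6 months | about 0.55-0.59 | about 70% |

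The exponential means are before selection on being alive at entry. With delayed entry the false-positive rate returns to about 4-7%, and in the large-sample runs the null HR returns to 0.97-1.01. The rates come from a few hundred to 1,000 simulations each, so differences of a few percentage points between rows are noise.

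**The case against.** The strongest reply is that late arrival is inferred. No section says that patients are referred, how late they come, or which treatments follow referral. The wording in 3.3 comes from a feasibility survey and is not a case-finding rule. The remark in 2.1, "Auto- and allo-geneic hematopoietic stem cell transplant is also reported in the salvage setting with variable success", is literature background and does not describe AMC practice. If sites find cases through their own diagnostic files, the bias is small. If late entry is spread evenly over treatments, survival is inflated but no treatment is favoured. All of this stands, and it makes the point conditional.

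Section 3.1 also requires stage at diagnosis, treatment, response and pathology material. HIV-positive cases need CD4 count and viral load from no later than 3 months after diagnosis. These requirements favour cases documented from diagnosis. They do not settle the question, because no text says that the records must come from the AMC site and outside records could supply them.

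A reader might infer three stronger things, none of which the documents support:
- **That the bias will occur and will favour referral-centre treatments.** The text permits late entry but does not state it, and the 70% figure needs a uniform 6-month delay and complete overlap of treatment and referral.
- **That the high expected share of long-term survivors shows truncation at work.** Even if every case entered at 6 months, this model gives 12.5%, below both of the plan's ranges. A long survival tail, or survivors known beforehand ("We are already aware of at least 10 long -term AIDS-PEL survivors within the AMC"), could explain the gap.
- **That the omission could never be repaired.** This is a chart review, so sites could be queried. Section 7.1 refers to dates of treatment and response, and the full case report form is not in the documents.

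**Conclusion.** The point holds in conditional form. As written, the plan can neither detect nor correct left truncation: survival runs from diagnosis, the methods are ordinary Kaplan-Meier and Cox, entry is not tied to diagnosis at the site, and the date first seen is not a listed item. If cases enter late, overall survival is overstated, and any treatment concentrated among them looks better than it is.

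The size is unknown. Under the assumptions above, the distortion of the treatment comparison runs from negligible (short delay, partial overlap) through moderate (14-32%) to severe only in the worst case. The effect on overall 2-year survival is modest in the scenarios with varying delays. Because the size cannot be judged from the planned data, and a primary objective depends on it, the change should be made before the data are collected. It is not a reason to regard the study as invalid.

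**What to change.** - **Data (4.2.1.1).** Add months from PEL diagnosis to first visit at the enrolling site, and months from diagnosis to the start of each treatment. Keep both out of the eligibility criteria in 3.1, so that no case is lost for lacking them.
- **Analysis (5.1.1).** State diagnosis as the time origin. Use delayed-entry risk sets for Kaplan-Meier and Cox. Analyse therapies started after diagnosis as time-dependent covariates or by landmark. Delayed entry alone does not remove the immortal time of a patient seen from diagnosis but treated later.
- **Sensitivity analysis.** Repeat the main analyses in cases diagnosed at the enrolling site, or first seen there shortly after diagnosis, with the window fixed in advance.

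The cost is two timing items from the chart and a few sentences of SAP text. Early risk sets become smaller, so intervals in the first months are somewhat wider.

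Two limits should be stated in the plan. Delayed entry assumes that entry time is independent of prognosis, given covariates, and referral because of failing treatment could break that assumption. It also does not correct selection from the requirement for known 2-year status or from survivors identified beforehand.

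### Section 5.1.1 plans Kaplan-Meier and Cox, but survival time is optional, the required 2-year status has no clinical analysis, and later-started treatment has no timing rule

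*Combined protocol and SAP*

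**What the plan says.** Section 1.2 sets the primary clinical objective as finding baseline characteristics and treatment strategies that correlate with survival of at least 2 years. Section 5.1.1 gives the clinical analysis in three sentences: Kaplan-Meier and Cox, response rates with confidence intervals, and descriptive statistics. The Cox sentence reads "Cox proportional hazards model will be used to assess differences between treatment groups and categorical baseline variables". The groups are not defined there or elsewhere.

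Section 3.1 admits patients "on whom survival status at 2 years post PEL diagnosis is available". Its minimum clinical data include treatment, "Response to PEL treatment" and 2-year status, but no survival time. Section 4.2.1.1 has the same gap. Survival time appears only in Section 4.2.1.3, as "Survival status at time of enrollment and duration of survival in months from PEL diagnosis", in a list headed as "additional data that is highly desirable for inclusion whenever available". That list also holds number of regimens, effusion drainage and antiretroviral drugs received after diagnosis. No list asks when a treatment started.

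Section 2.1 describes strategies that can begin late, among them "methotrexate (after chemotherapeutic debulking or drainage of effusions") and transplant: "Auto- and allo-geneic hematopoietic stem cell transplant is also reported in the salvage setting with variable success". It also says "PEL is typically associated with a poor prognosis with a median survival of 6 months".

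**The concern.** Three gaps meet in one short section.

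- **Method and required data do not match.** Kaplan-Meier and Cox need a time to death or last contact. A patient with only the required data has a status at 2 years and, if dead, no event time. No handling rule is given.
- **Outcome and method do not match.** The outcome that Objective 1 names, and that every eligible patient has, is not the subject of any stated analysis of clinical factors.
- **Later treatment has no timing rule.** Survival is counted from PEL diagnosis. If a treatment that starts months later is coded as a fixed group, the time a patient had to survive to receive it is credited to the treatment. With a 6-month median, a few months is a large credit.

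Treatment strategies are half of Objective 1, and Section 2.2 hopes the findings may lead to prospective studies. Start and death times not abstracted during chart review cannot be supplied by a later analysis.

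**Working it through.** **1. Required data against planned method**

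| Item | Where | Status |
|---|---|---|
| Vital status at 2 years | 3.1, 4.2.1.1 | Required; no clinical-factor analysis uses it |
| Months of survival from diagnosis | 4.2.1.3 | Optional; needed by Kaplan-Meier and Cox |
| Treatment of PEL | 3.1, 4.2.1.1 | Required; not grouped |
| Treatment start time | not listed | Needed to place later treatment in time |

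The explicit contrast of 10 long-term with 10 other survivors in Section 4.3.2.1 belongs to the genomic objective.

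**2. Survivors and deaths expected.** Section 4.3.1 expects 25-40% long-term survivors: 80 × 0.25 = 20 and 80 × 0.40 = 32, which reproduces its 20-32. Section 5.2 expects 15-25%: 80 × 0.15 = 12 and 80 × 0.25 = 20. Deaths by 2 years are therefore 48-60 on the first estimate and 60-68 on the second.

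**3. Missing death times.** The rate m of deaths without a time is not in the documents; I assume 10% and 30%. If survivors without a duration are censored at 24 months while undated deaths are dropped, observed 2-year survival is 80S / (80 − m × 80(1 − S)):

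- S = 15%: 12/73.2 = 16.4%; 12/59.6 = 20.1%
- S = 25%: 20/74 = 27.0%; 20/62 = 32.3%
- S = 40%: 32/75.2 = 42.6%; 32/65.6 = 48.8%

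If every record without a duration is dropped, and durations are missing equally often in deaths and survivors, there is no bias, only fewer patients.

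**4. Later treatment coded as a fixed group.** This is a simulation with no true effect, in treated patients only. From the documents: n = 80, median 6 months, 2-year survival of 15-25% or 40%. Assumed: start windows, share of patients planned for the later item, first-line start uniform over 0-0.5 month (deaths before it excluded), censoring at 60 months. All curves pass through S(6) = 0.50. They are Weibull (15%: shape 0.73; 25%: shape 0.50) or a long-term-survivor mixture p + (1 − p)exp(−λt), with p = 0.12, 0.24 and 0.40 for 15%, 25% and 40%. The last column also requires survival to 2 months, as a stand-in for early deaths failing the response requirement in Section 3.1.

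| Later item: start; planned share | HR at 15-25% (40%) | HR if deaths before 2 months are out |
|---|---|---|
| 1-2 months; 30% | 0.74-0.80 (0.64) | 1.00 (1.00) |
| 1-4 months; 20% | 0.66-0.73 (0.53) | 0.89-0.92 (0.81) |
| 1-4 months; 50% | 0.56-0.63 (0.42) | 0.82-0.88 (0.74) |
| 3-9 months; 50% | 0.32-0.47 (0.18) | 0.43-0.60 |

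Repeat runs agree to about 0.01. With early deaths kept, false positives at nominal 5% run from 10-16% (20%) in the first row to 88-97% (over 99%) in the last. With early deaths out, they are about 4-7% in the second row and 8-11% (15%) in the third. A time-dependent covariate gives HR 0.99-1.01 and a landmark 0.98-1.03. Two null first-line regimens with the same start give 1.00-1.01.

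**5. Precision of a 2-year status analysis.** Exact (Clopper-Pearson) 95% intervals: 12/80, 8-25%; 20/80, 16-36%; 32/80, 29-52%.

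**The case against.** The strongest reply is that the plan is brief, not wrong. This is a retrospective case series. Sections 1.1 and 2.1 say that long- and short-term survivors will be compared, a Kaplan-Meier curve can be read at 24 months, and Cox is a defensible way to relate factors to survival without dichotomising. That stands as far as it goes. But no method is attached to the comparison, reading a curve at 24 months does not test factors, and either route needs the optional survival time.

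The second reply is that no bias has been shown. A reader might infer that the study will make an ineffective later treatment look protective. The documents do not support that. They never say later treatments will be fixed groups; methotrexate after debulking and salvage transplant appear as background. The required item is simply treatment, and a first-line grouping would be unaffected. If the response requirement removes early deaths, which Section 3.1 does not settle, the hazard ratios for starts within 4 months move close to 1 or reach it. Only the 3-9 month window stays large, and no passage supports that window or a 50% share. Treatment given for progression can push the other way. All of this stands and limits the claim about size.

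A treated-versus-untreated contrast would give far more extreme ratios, but never-treated patients may be outside the set because response is required, so the point does not rest on it.

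Third, duration is already on the collection list. True, but as an optional item; treatment start is not listed at all.

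**Conclusion.** The point holds as a mismatch between objective, required data and method, and should be fixed. Followed with only its required data, the plan leaves some eligible deaths out of its sole clinical survival analysis, does not analyse the required 2-year status against clinical factors, and cannot place later treatment in time.

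The size is not established. The hazard ratios and false-positive rates are conditional illustrations. They rest on assumed start windows and shares, on whether early deaths meet the response requirement, and on fixed coding that the plan does not state. The net direction in the real data is unknown. A reader might also infer that 2-year survival will be overstated. That follows only under the asymmetric handling in step 3, which the plan does not prescribe, and at a missing rate that nobody knows.

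**What to change.** 1. **Section 5.1.1, Objective 1.** Add an analysis of 2-year status by baseline factor and first-line treatment in all eligible clinical-portion patients, with exact 95% confidence intervals and exact tests or a small logistic model. It needs no death date. Reconcile the survivor estimates in Sections 5.2 and 4.3.1, since they decide how small the model must be.
2. **Section 4.2.1.1, data.** Make months from diagnosis to death or last contact, and to the start of each treatment, required CRF items with unknown as a permitted answer, and not eligibility conditions. Report how many deaths lack a time, and treat them as interval-censored (0-24 months) in a sensitivity analysis. In Kaplan-Meier and Cox, apply the same rule to deaths and survivors without a duration.
3. **Section 5.1.1, treatment.** Define the groups. Use ordinary Cox for variables known at diagnosis and for first-line groups with comparable start times. For later treatment use a time-dependent covariate, with a landmark at one pre-stated time as a check. Report patients with an unknown start time separately, and state that confounding by indication remains.

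The cost is an amendment with IRB approval at each institution (Section 7.2) and a little more chart review. Section 7.1 may intend years only and does not name death among its dates, so intervals in months, the form Section 4.2.1.3 already uses for survival, are the easier request. Required fields reduce missing times but do not remove them. A landmark drops early deaths: in the simulation about 61-65 of 80 remain at 2 months, 49-52 at 4 months and 31-39 at 9 months. The 2-year estimates will be imprecise, as step 5 shows.
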